Baseline and Study Procedures: After screening, subjects will undergo fMRI and behavioral assessments at baseline followed by stratification by sex and double-blind randomization to either bupropion XL 150mg/d or escitalopram 10mg/d as indicated in Table 1. The randomization scheme will be implemented by research pharmacy, and all patients and study staff will be blinded to treatment assignment. Patients will be randomized in blocks of 4. After 2 weeks, subjects with a HDRS-17_>7_will be increased to bupropion XL 300mg/d or escitalopram 20mg/d as tolerated. fMRI scanning and behavioral assessments will be repeated at 4 and 8 weeks. Vital signs, safety labs, urine toxicology and adverse events will be collected as indicated in Table 1. The primary outcome (Aim 1) will be targeted VS-vmPFC FC as detailed below. Secondary outcomes (Aim 2) will include RDoC positive valence constructs including objective assessments of effort-based decision making and clinician-administered and self-report assessments of motivation/anhedonia (see below). Additional (exploratory) outcomes will include treatment response over time and adverse events.

Table 1. Schedule of Study Procedures and Assessments

	Virtual	Visit 1 Screen	Visit 2		Visit 3	Visit 4	Visit 5	Virtual	Visit 6
Assessments	Intake		Screen B	Base- line A	Base- line B		Wk 4	Wk 6	Wk 8
Consent	Х								
PHQ-9, Medical / Psychiatric Screening***	Х	[X]	[X]						
FERN MRI Screening Form***	[X]	х					Х		Х
ATRQ, Medical History, SCID V-modified (Mood, Anxiety, PTSD modules), Bipolarity index	X								
Laboratory Eval*, Urinalysis, height weight***		Х							
Rapid CRP (Finger Stick)***		Х	Х						
Physical Exam			Х						
Vital Signs		Х	Х		Х	Х	Х		Х
Adverse events**, Concomitant Meds***	Х	Х	Х		Х	Х	Х	х	Х
Urine toxicology screen, pregnancy test***		Х		 	Х		Х		Х
Research bloods†				Х			Х		Х
Neurocognitive Battery				Х		Х	Х		Х
EEfRT (computer-based)				Х	Х	Х	Х		Х
Demographics, habits, CTQ				Х					
MAP, IDS-SR, STAI, BAI, PCL-5, PSS				Х		Х	Х	Х	Х
fMRI					Х		Х		Х
SHAPS-C, CSSRS, CGI					х	Х	Х	Х	Х
HAM-A [Baseline only]****, HAM-D-17					Х	Х	Х		Х
Randomization to bupropion / escitalopram					х				

PI: [name] Sponsor: NIMH

Medication dispensing /compliance check§			Х	Х	Х	Х	Х
Adjustment of medication#				Х	Х	Х	
Discharge/discharge planning					Х	Х	Х

^{*} Laboratory evaluation will include the comprehensive metabolic panel, thyroid-stimulating hormone (TSH), CBC with diff, and plasma CRP.

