Aim 1: To determine whether bupropion (vs escitalopram) will increase FC in reward circuitry. Hypothesis 1: Bupropion vs escitalopram will increase VS-vmPFC FC in depressed patients with high CRP and anhedonia at baseline. Primary Endpoint: Targeted VS-vmPFC FC at 8 weeks. Predictors: group (bupropion vs escitalopram), time (baseline, 8 weeks), and group x time interactions. Covariates: Primary: Age, sex, BMI, race. Additional covariates: Number of depressive episodes, length of current depressive episode (in months), treatment trials (ATRQ), age of onset, and family history of depression (ves/no), weeks on targeted dose of medication, Analysis Plan: Subjects will be randomized to two different treatment groups and scanned across two visits. Consequently, a factorial mixed-effects models for repeated measures (MMRM) will be employed with group, time and group x time interaction on targeted VS-vmPFC FC as fixed effects and each subject's baseline (identity) as random effects. Linear and multi-level mixed effects will be evaluated using both unstructured and autoregressive covariance structures and restricted maximum likelihood estimation and will be used to predict random effects (slope and intercept) in addition to fixed effects, optimized using Bayesian Information Criteria (BIC). Primary and additional covariates will be entered in all models as random variables after testing for significant associations. Given the inherently noisy nature of the covariates, model tuning to optimize the balance between explanatory (r²) and noise variables (root mean square error) will be undertaken to select the most parsimonious models using BIC. The MMRM will also be augmented using Elastic net generalized regression models using group||time nesting approaches. Models will be selected using model comparison metrics. All analyses will be conducted in accordance with published guidelines.⁷⁶ Exploratory analysis: A similar analysis as indicated above will be conducted on fMRI scans conducted at 4 weeks. The 4-week scan will be conducted based on the rapid effects seen with dopamine agonists in our preliminary studies with L-dopa (data not shown).

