Aim 2. To determine whether bupropion (vs escitalopram) will improve motivational deficits. *Hypothesis 2a:* Bupropion vs escitalopram will improve objective and clinical assessments of motivation in depressed patients with high CRP and anhedonia at baseline. *Secondary Endpoints:* EEfRT, SHAPS-C and MAP. *Predictors and Covariates:* Same as above. *Analysis plan:* MMRM with random intercepts will be used to examine effects of group, time and group x time interaction controlling for variations in baseline scores. Relevant covariates as indicated in Aim 1 will be included in these analyses as described above.

Hypothesis 2b: Improvement in VS-vmPFC FC will correlate with improved objective and clinical assessments of motivation. Analysis plan: Multivariate regression models will be used to examine linear associations between primary (VS-vmPFC FC) and secondary endpoints (EEfRT, SHAPS-C and MAP). Models will be adjusted for relevant covariates as indicated above. Separate analyses will be run for each behavioral outcome of motivation. Type I errors as a result of multiple testing will be controlled by Family-Wise Error correction.⁷⁷

Aim 3. To determine whether bupropion (vs escitalopram) will improve depression severity. Hypothesis 3 (Exploratory): Bupropion vs escitalopram will improve depressive symptoms in MD patients with baseline high CRP and anhedonia. Analysis plan: MMRM will be used to examine effects of group, time and their interaction on depression severity using the HAM-D-17. Relevant covariates as in Aim1 will be included.

Interim Analysis: After 16 subjects have completed the study, the blind will be broken by [name], and an effect size estimation will be made of between group differences in VS-vmPFC FC.* If the effect size is less than Cohen's d =0.3 at both fMRI time points (weeks 4 and 8), the study will be terminated. If the effect size is between a Cohen's d of 0.3 and 0.6 at either 4 or 8 weeks, the study will be continued

PI: [name] Sponsor: NIMH

focusing on the fMRI time point with the largest effect size. If the between group difference in VS-vmPFC FC is >0.6 (Cohen's d), the possibility of using the data as proof-of-concept for a larger trial will be discussed with the study sponsor (NIMH).

* Due to slow recruitment secondary to COVID 19, we have decided to conduct the interim analysis at 16 subjects as opposed to 20.

11. Power Analysis

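### Covariates are to enter as random terms, chosen by testing and with no time interaction, and sex, the randomisation stratum, has no assured place in the primary test

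*Combined protocol and SAP*

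**What the plan says.** All of this is in the combined protocol and SAP.

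- **Model (section 10, Aim 1).** The model takes "group, time and group x time interaction on targeted VS-vmPFC FC as fixed effects" and "each subject's baseline (identity) as random effects". The predictors include "time (baseline, 8 weeks), and group x time interactions", so the primary model has two visits and baseline is one level of time.
- **Covariates (same paragraph).** The primary list reads "Covariates: Primary: Age, sex, BMI, race". A longer additional list includes "weeks on targeted dose of medication".
- **Entry rule (same paragraph).** "Primary and additional covariates will be entered in all models as random variables after testing for significant associations". The plan then tunes the model towards parsimony by BIC and adds an elastic net. The entry sentence is at odds with itself: it promises entry in every model, yet makes entry follow a test. It gives neither the outcome nor the threshold of that test.
- **Stratification (section 5, Baseline and Study Procedures; also Specific Aim 1 in section 4).** Baseline assessments are "followed by stratification by sex and double-blind randomization", in blocks of 4. No sentence says that sex stays in the analysis.
- **Other aims (section 10).** For Hypothesis 2a: "Relevant covariates as indicated in Aim 1 will be included in these analyses as described above". Aim 3 refers to the Aim 1 covariates in the same way.

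**The concern.** There are three separate defects.

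1. **Form.** A random effect needs a population of levels from which a variance can be estimated. Sex has two levels. Age and BMI have nearly one level per patient, so as random factors they cannot be told apart from the patient effect already in the model. Race is a small set of named categories.
2. **No route to the treatment test.** Age, sex, BMI and race do not change within a patient, and the group-by-time term is a within-patient contrast. Without a time interaction these covariates have nothing to act on. A reader who sees four primary covariates listed would think the Hypothesis 1 result is adjusted for them.
3. **Selection of the stratum.** Stratified randomisation balances the arms on sex. The precision this buys reaches the test only if sex is in the model as a predictor of change. A significance screen followed by BIC leaves that to the data.

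At stake are a correct description of the primary analysis and some power in a trial planned on 40 completers. The validity of the type I error is not at stake.

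**Working it through.** **Inputs.** From section 11, Hypothesis 1: change in FC 0.20 (SD 0.16) for bupropion and 0.07 (SD 0.10) for escitalopram; alpha 0.05; power above 0.80; d = 0.97; 36 patients required, 40 planned. From section 5: 50 randomised, blocks of 4 within sex. Assumed, because the documents are silent: a two-sided test, the share R² of the variance in FC change that sex explains, and the sex mix (26 of 40 in one sex).

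**1. The plan's own figure.** d = (0.20 − 0.07) / √((0.16² + 0.10²)/2) = 0.13 / √0.0178 = 0.974. A two-sided two-sample t-test on change then needs 17.7, so 18 per arm, 36 in total. Power is 80.7% at 18 per arm and 84.8% at 20 per arm. The stated sample size reproduces.

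**2. Why the covariates cancel.** Write patient i's FC at visit t (0 = baseline, 1 = week 8) as

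y(i,t) = α + βG(i) + τt + δG(i)t + γ′x(i) + u(i) + e(i,t).

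Subtracting the visits gives y(i,1) − y(i,0) = τ + δG(i) + e(i,1) − e(i,0). The covariate term γ′x(i) and the patient effect u(i) both drop out. Treating γ as fixed or random makes no difference. With γ₂′x(i)t added, γ₂′x(i) stays in the difference.

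**3. Check on one simulated data set** (40 patients, two visits, REML), group-by-time term:

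| Model | Estimate | SE | z |
|---|---|---|---|
| No covariates | 0.0925 | 0.0392 | 2.362 |
| Sex, or all four primary covariates, as fixed main effects | 0.0925 | 0.0392 | 2.362 |
| Random age coefficient | 0.0925 | 0.0392 | 2.362 |
| Sex by time added | 0.0925 | 0.0395 | 2.341 |
| Four covariates by time added | 0.0930 | 0.0426 | 2.181 |

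The t-test on change gives the first row exactly. So does an unstructured covariance, with or without sex and age as main effects. One fit departed: random age and sex coefficients together kept the estimate but gave SE 0.0383. That model is over-parameterised for two observations per patient, which is a further reason not to use the random form.

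**4. Leaving sex out of the test on change.** 20,000 simulated trials per row, blocks of 4 within sex, 40 patients, d = 0.97 on the SD of observed change:

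| R² of sex (assumed) | Type I error, sex out | Type I error, sex in | Power, sex out | Power, sex in | Forgone (points) |
|---|---|---|---|---|---|
| 0 | 4.8% | 4.8% | 84.6% | 84.5% | about 0 |
| 0.05 | 4.4% | 4.8% | 85.1% | 86.2% | 1.1 |
| 0.10 | 3.9% | 4.8% | 85.6% | 88.0% | 2.4 |
| 0.20 | 3.0% | 4.8% | 86.8% | 91.3% | 4.5 |

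A separate simulation gave type I errors without sex of about 4.3%, 3.7% and 2.8% at R² of 0.05, 0.10 and 0.20.

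The noncentral t gives the same power with sex in. With noncentrality 0.97·√(20/2)/√(1 − R²) and 37 degrees of freedom, power is 84.8%, 86.5%, 88.3% and 91.6% down the four rows.

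**5. How often a screen would keep sex.** If the screen tested sex against FC change at p < 0.05 (an assumption), sex would be kept in about 29% of trials at R² = 0.05 and 54% at R² = 0.10.

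**The case against.** A reader might infer more than the documents support. Five stronger readings should be set aside.

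- **That random entry or the significance screen causes the cancellation.** It does not. Ordinary fixed main effects cancel in the same way. The cause is two visits with no time interaction, so deleting the quoted words alone would leave the group-by-time result as it is.
- **That adjustment can never move the primary result.** The paragraph on targeted FC in section 5 says change from baseline will be calculated, and section 11 powers the trial on change. In a change-score model or an ANCOVA on week-8 FC, covariate main effects do act. Other routes exist too. Weeks on targeted dose, coded over time, moved the simulated estimate from 0.0925 to 0.1000. With 20% of week-8 scans missing, the four main effects moved it from 0.0809 to 0.0815. The elastic net is another route.
- **That omitting sex inflates error or pulls power below plan.** It does neither. The protocol's d rests on SDs of observed change, which already contain any variance due to sex. Power without sex is therefore never below the figure for no sex effect.
- **That sex will be dropped.** The sentence also says covariates enter all models, and the screen is undefined. The documents show only that sex has no guarantee.
- **That the exact cancellation carries into Aims 2 and 3.** Hypothesis 2a controls for baseline scores and Hypothesis 2b is a regression, so covariates can act there. Only the entry and selection wording carries over.

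It is also fair to say that nothing in the documents shows that sex predicts FC change. If it does not, omitting it costs nothing. What stands is that the form is unsuitable, the selection is data-driven, and the stratum has no assured place.

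**Conclusion.** The point holds in this limited form. The covariate rule is not a usable specification. In the two-visit model with complete scans, the four primary covariates contribute nothing to the treatment test, because no time interaction is named. Sex may be left out although the trial randomises by it.

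The harm is modest. If sex explains 5 to 20% of the variance in FC change, the test without it is conservative (type I error about 4.3% falling to 2.8%) and forgoes about 1 to 5 points of power at d = 0.97. There is no bias and no inflated error. These sizes rest on the assumed R² range, a two-sided test and 40 complete patients. The change is worth making because it costs almost nothing.

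**What to change.** 1. In every treatment comparison, always include sex as a fixed effect that acts on change, whatever its p-value or BIC. In the two-visit model this means sex and sex by time. In an ANCOVA on week-8 FC or a change-score model, a sex main effect is enough.
2. Name in advance any other primary baseline covariate that is wanted and enter it the same way. Otherwise remove the statement that the model adjusts for it.
3. For the primary model, delete the clause that makes covariates random and conditional on a significance test, and exempt the named covariates from BIC selection.
4. In Aims 2 and 3, replace the cross-references to the Aim 1 rule with the same fixed entry of sex in the treatment comparisons.

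**Cost.** The change is wording, plus one degree of freedom for sex. If sex explains nothing, power at 40 completers is 84.5% with sex and 84.6% without in the simulation. The required sample size does not rise: 36 completers with four covariate degrees of freedom still give 80.4% power when the covariates explain nothing.

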Hypothesis 1: Our preliminary data from depressed (major depression – MD) patients with high inflammation (CRP >2 mg/L, n=7) administered a dopaminergic agent, L-DOPA, and placebo control was used to estimate the anticipated change in VS-vmPFC FC in response to treatment (bupropion) and control (escitalopram) conditions in the proposed study. The expected change in FC in response to bupropion and escitalopram (the withinsubject effects of these conditions) was then used to calculate the effect size (ES) and sample size per group that will be required to detect a significant difference between the response to bupropion versus escitalopram (the between-subjects effect) with alpha= 0.05 and power >0.80. Accordingly, based on the mean and standard deviation for the change in FC after L-DOPA (0.2±0.16), we can expect a large ES for the expected within-subject effects of bupropion (Cohen's $d_7 = 1.25$, which would require only 8 subjects to detect). Based

Figure 1: Estimated power for between-subject comparisons of the FC response to bupropion versus escitalopram. Sample size (x-axis) and power (y-axis) for ES (d) = 0.97. The proposed total sample size of 40 (dashed line, n=20 per group) will yeild power >0.8.

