on the mean and standard deviation for the change in FC after placebo (0.07±0.10), we expected a medium effect size for the effects of escitalopram (Cohen's d₂ = 0.7), representing ~30-40% increase in FC and consistent with a ~30% placebo effect commonly observed in trials in MD patients.⁷⁸ Based on these expected within-subject effects for our treatment and control groups and the corresponding mean and standard deviations from our preliminary data, we estimate the between-group effect of the response to bupropion and response to escitalopram to have an ES Cohen's d = 0.97, which would require a total sample size of 36 (18 per group) for power >0.8 at alpha=0.05. Using 5000-fold resampling, with alpha = 0.05, sample power= 0.8, sample sizes of 18 per group (total sample size= 36) was large enough to estimate group differences. Figure 1 presents a graphical representation of the total sample sizes required for between-subject group comparisons of the FC response to bupropion versus escitalopram across the full range of power, demonstrating >80% power at the proposed total sample size of n=40. Hypothesis 2: For hypothesis 2a, the expect difference in motivation after bupropion versus escitalopram is based on the improvement in the EEfRT that has been previously established to be clinically and pharmacologically meaningful (≥10% change, 79, 80 representing a 0.10 increase in probability of hard choice choices) and standard deviations from our preliminary data for the EEfRT in MD patients. Thus, we expect a 0.10 ± 0.10 difference in mean probability of hard choices after bupropion compared to placebo and a medium to large ES (Cohen's d = 1.0), which will require a total sample size of 34 subjects (17 per group) for power >0.8 at alpha=0.05. For hypothesis 2b, our preliminary data on the relationship between VS-vmPFC FC and motivation, as measured by the EEfRT, demonstrated a correlation coefficient (r) of 0.43 (r² = 0.185). We expect a similar effect size for the relationship between change of FC and change in motivation and will need a sample size of 37 subjects to detect an overall relationship between change in FC and motivation with power >0.8 at alpha=0.05. Therefore, based on our sample size of n=40 (20 per group) we will have at least 80% power to detect significant differences for the proposed hypotheses to be tested under both Aims 1 and 2 at alpha=0.05.

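### The plan names a core mixed model for Hypothesis 1 but lets the data choose its final form, so no single model and contrast decides the test and the stated alpha and power are not assured

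*Combined protocol and SAP*

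**What the plan says.** Section 10, Aim 1, sets targeted VS-vmPFC connectivity at 8 weeks as the primary endpoint. The core model is an MMRM with group, time (baseline and week 8) and their interaction as fixed effects. The same paragraph then reopens that model in four ways.

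- **Covariance.** The fits use "both unstructured and autoregressive covariance structures and restricted maximum likelihood estimation", optimised by BIC.
- **Covariates.** There are four primary and six additional candidates, ten in all. They enter after a test for association, and tuning "will be undertaken to select the most parsimonious models using BIC". They are described as entering as random variables. One of the ten, time on the targeted dose, is measured after randomisation.
- **Elastic net.** "The MMRM will also be augmented using Elastic net generalized regression models using group||time nesting approaches". The penalised terms, the mixing parameter, the tuning rule and the nesting notation are not defined.
- **Final choice.** "Models will be selected using model comparison metrics". The metrics are not named.

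All of this comes before the exploratory label in that paragraph, which covers only the 4-week scan. Aims 2 and 3 reuse the Aim 1 covariates. The interim analysis in section 10 breaks the blind after 16 completers, when "an effect size estimation will be made of between group differences in VS-vmPFC FC". Section 11 sizes the trial "with alpha= 0.05 and power >0.80" for a two-group comparison of change and includes no selection step.

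**The concern.** When fit criteria choose the model from the trial data, the reported standard error is computed as if that model had been fixed beforehand. It can then be too small, and the test can reject too often.

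Two of the tools named also carry risks of their own. REML likelihoods cannot be compared between models with different fixed effects. A penalised regression can shrink or remove the treatment coefficient.

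At stake is whether the nominal 5% level, the stated power and the estimated drug effect describe the analysis that will actually be reported for the primary hypothesis. The trial is meant to supply foundational data for larger ones, so the effect estimate matters as much as the p-value.

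**Working it through.** **1. The plan's own figure.** Section 11 gives "change in FC after L-DOPA (0.2±0.16") and "change in FC after placebo (0.07±0.10").

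- Pooled SD = √((0.16² + 0.10²)/2) = √0.0178 = 0.1334.
- d = (0.20 − 0.07)/0.1334 = 0.974, against 0.97 stated.
- A two-sided t-test at 0.05 (noncentral t) needs 18 per group, 36 in total, with power 80.7%. At 20 per group the power is 84.8%.

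Sidedness is not stated; a one-sided test would need only 14 per group, so two-sided is what the plan used. The stated size is reproduced for one fixed comparison of change.

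**2. What the choice of model does not affect.** One simulated data set with both visits complete (20 per arm) was fitted by REML under unstructured and AR(1) covariance, with and without four time-constant covariates as fixed main effects. All four fits gave the same group × time estimate (0.0634) and standard error (0.0471), equal to the change-score test. Terms that are constant within a subject cancel in the within-subject difference.

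**3. Selection that acts on the change.** Section 5 has change from baseline in connectivity calculated, so covariates could be related to it. The simulation assumed 20 per arm, SD 0.1334 and no drug effect. Ten candidates, all treated as baseline measures, explained 0% or 30% of variance. There were 3,000 runs per setting, so the Monte Carlo SE is √(0.05 × 0.95/3000) = 0.4 points.

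| Analysis | Type I error, 0% | Type I error, 30% |
|---|---|---|
| One fixed test (unadjusted) | 4.8% | 5.3% |
| Univariate screen at p<0.05 | 4.8% | 5.3% |
| Forward BIC, group forced in | 6.5% | 8.3% |

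A separate stepwise-BIC simulation with ten candidates (4,000 runs) gave 6.6% with covariates explaining 0% and 8.0% with 20%. Another forward-BIC check gave 7.5 to 9.3%. Overall this is roughly 6.5 to 9%.

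**4. BIC from REML fits, if covariates are fixed effects.** One simulated data set and one covariate gave −2 log REML of −55.05 in months and −60.02 in years. The gap is 2 ln 12 = 4.97. BIC's penalty for one term is ln 40 = 3.69 (subjects) or ln 80 = 4.38 (observations), so a change of unit can outweigh it. Maximum likelihood gave −86.31 in both units. In the data of step 2, multiplying four covariates by 100 moved REML-BIC from −176.05 to −139.20. That shift is 2 × 4 × ln 100 = 36.84 up to rounding, and the treatment contrast did not change. The plan lists episode length in months.

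**5. Elastic net, if it penalises group.** Mixing 0.5 and BIC tuning are assumed. The true difference is 0.13, with 1,500 runs per setting.

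| | Covariates explain 0% | Covariates explain 30% |
|---|---|---|
| Mean estimate | 0.061 | 0.084 |
| Shrinkage, 1 − estimate/0.13 | 53% | 35% |
| Group dropped | 33% | 16% |
| Power after refit | 66% | 80% |
| Power, unadjusted test | 86% | 85% |

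Under no effect, the refitted test rejected in 1.2% and 4.5% of runs. The harm here is to power and the estimate, not to type I error.

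**The case against.** The case on the other side is substantial, and much of it stands.

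- **There is a test.** Endpoint, time points and the group × time term are named. A reader might infer that Hypothesis 1 has no test at all; the text does not support that. What is missing is the statement that this contrast, from one specified model, decides the hypothesis.
- **The treatment term may not be penalised.** A reader might infer that the elastic net penalises it. The text does not say so, and augmenting the MMRM need not mean replacing it. Step 5 is therefore conditional.
- **REML with BIC can be legitimate.** It is mentioned alongside covariance structures and random effects, where the fixed effects may be constant. If covariates really enter as random variables, the unit problem disappears. Step 4 needs fixed coefficients, which is the usual treatment of age, sex or BMI.
- **The contrast is robust in the simplest case.** Step 2 shows this, and no covariate × time term is listed. The entry rule that is named, a test for association, holds about 5% when used alone. Forward or stepwise selection is an assumed way of carrying out the BIC pruning.
- **The interim look.** A reader might infer that the unblinded estimate will steer the tuning. The plan does not say so; it is only silent on whether the model is locked first.

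What remains is that the selection steps sit inside the primary plan, are not labelled as sensitivity work, and end in a choice by unnamed metrics.

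**Conclusion.** The point holds in a limited form. The final Aim 1 model is chosen from the data and no single model and contrast is designated, so section 11's alpha and power, which belong to one fixed comparison of change, are not assured for the procedure in section 10.

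The likely type I error is roughly 6.5 to 9% rather than 5%. That range assumes forward or stepwise BIC selection on the change in connectivity with group forced in, and covariate strengths that the documents do not give. With both visits complete, the plain group × time contrast is unaffected by covariance structure or time-constant main effects. Missing scans (10 of 50 projected) were not simulated. The REML and elastic-net problems are real only under the conditions given above.

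A reader might go further and infer that any significant model would be reported. Across seven candidate analyses that would give 9.1 to 11.7%. The plan selects on model metrics, not on the significance of the drug effect, so those figures should not be cited as its error rate. Nor do the documents support saying that neither the error rate nor the estimate can be trusted at all. For a pilot with moderate, conditional inflation and a wording-only remedy, this should be fixed but is not fatal.

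**What to change.** Designate one model as the sole test of Hypothesis 1. The contrast should be either the group difference in change from baseline to week 8 or a baseline-adjusted group difference at week 8, reported with its confidence interval. Specify one covariance structure and a fixed list of baseline covariates entered as fixed effects. Leave time on the targeted dose off that list, because it arises after randomisation.

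Lock the model before the final unblinded analysis, and before the interim look if that has not yet taken place.

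Label BIC tuning as sensitivity or exploratory work, using maximum likelihood whenever the fixed effects differ. Do the same for the elastic net, with group, time and group × time left unpenalised and no treatment p-value taken from it.

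The cost is SAP wording and the freedom to tune the primary model. The sample size stays as stated, 36 needed and 40 planned. In the simulation the fixed test held about 5% type I error and gave a mean estimate of 0.131 for a true 0.13; power at 20 per group is 84.8%.
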